6.2.5 Follow-up Assessments

All subjects will have follow-up assessments irrespective whether they discontinue study interventions or are non-compliant with interventions or use off-protocol treatments.

Follow-up Assessment at End of Treatment (weeks 8-10 depending on whether subject had fMRI): A subject visit will be arranged by study personnel for the post-treatment (end of counseling/hypnotherapy session) assessments which should occur within 2 weeks of finishing the treatment sessions for those subjects not undergoing fMRI or within 3 weeks of finishing treatment for those who will also undergo a follow-up fMRI. Subjects may have urine and vaginal swab samples collected and stored for possible future analysis (For example, urine may be analyzed for biomarkers).

The assessments and visit will include

- Questionnaires; OABq-SF, ISI, PPBC, PISQ-12, CRADI-8, IBS Module, and IC questionnaire. Follow-up Expectation Question and Compliance Questionnaire
- Voiding Diary
- Subject feedback regarding study participation
- Confirm subject contact information (patient email address, mailing address, cell and landline phone numbers, name/address/phone number of friend or relative in event of difficulty contacting patient)
- Confirm arrangements for patient incentive payments and for follow-up in 6 months

6 month Follow-up (month 6) the Study Coordinator or her designee will arrange 6 month follow-up assessment visits for subjects. Although it is preferable to have an in-person visit, it is possible to have the visit performed via phone and mail. Patient reimbursements will be paid at the in-person visit. If the subject has a phone/mail visit arrangements for reimbursement will be made following completion of this visit. The follow-up assessment should be completed within 5-7 months of completion of hypnotherapy or pharmacotherapy sessions.

Final assessments & follow-up include

- Questionnaires; OABq-SF, ISI, PPBC, PISQ-12, CRADI-8, IBS Module and IC questionnaire. Follow-up Expectation Question and Compliance Questionnaire
- Voiding Diary
- Subject feedback regarding study participation
- Confirm subject contact information (patient email address, mailing address, cell and landline phone numbers, name/address/phone number of friend or relative in event of difficulty contacting patient)
- · Confirm arrangements for patient reimbursement and for follow-up at 12 months

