9.1 General Design Issues

This study includes

- 1. A single-blinded, randomized controlled trial (RCT) based on a non-inferiority design which compares hypnotherapy to pharmacotherapy in treating UUI.
 - Urge incontinent women (N=152) will be randomized to hypnotherapy or pharmacotherapy and evaluated at months 2, 6 &12
- 2. Both a cross sectional study and RCT which will evaluate up to 80 of these women with UUI.
 - These women will undergo fMRI before treatment and their baseline imaging results will be compared to normative controls.
 - In addition, the UUI subjects participating in the fMRI will undergo imaging after treatment. The images of UUI subjects following treatment will be compared to their baseline images.

Specific Aims, Hypotheses and Outcomes;

Primary Outcomes:

- 1. Between group differences in change in UUI episodes for Specific Aim 1 at 2 month follow-up based on 3 day voiding diaries
- 2. Between group differences in change in activation of limbic cortex and brain connectivity following treatment for Specific Aim 2

Secondary Outcomes:

- 1. Between group differences in change in UUI episodes for Specific Aim 1 from baseline to follow-up at both 6 and 12 months based on 3 day voiding diaries.
- Between group differences in change in pad counts, voiding frequency and cure (resolution) of UUI on voiding diary for Specific Aim 1 at 2, 6 and 12 month follow-up as well as "durable cure" (resolution of UUI on all follow-up diaries at 2, 6 & 12 months)
- 3. Between group differences in the follow-up expectation question and between group differences in questionnaire change scores (the OAB-qSF, ISI, PISQ-12, Global questionnaire, CRADI-8, IBS Module, IC questionnaire) for Specific Aim 1 at 2, 6 and 12 month follow-up
- 4. Baseline differences in activation of the limbic cortex and brain connectivity in women with UUI compared to normative controls for Specific Aim 2

1. Specific Aim 1: Determine whether a mind/body therapy (hypnotherapy) is as, or is more effective and durable, in treating urgency urinary incontinence (UUI) than a non-mind/body treatment (pharmacotherapy) Hypothesis: Among patients with urgency urinary incontinence, hypnotherapy ameliorates abnormal perception of bladder distension outside the hypnotic state and thereby diminishes symptoms of urgency and decreases incontinence as effectively as (or more effectively than) pharmacotherapy

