We anticipate that missing data will be generated in two primary ways; 1) Small numbers of subjects may withdraw consent or be lost to follow-up and will not have any measurements after their withdrawal. In this case, the study will be missing all data and these will be censored observations. The missing data may fall across the spectrum from missing completely at random to missing not at random 2) Subjects may fail to provide data at a specific follow-up time due to unforeseen life-events (illness, family emergencies) that do not allow them to provide assessments within the allowable window. The missing data from this second group will follow an intermittent pattern. Again, the missing data may fall across the spectrum from missing completely at random to missing not at random.

We will use two general strategies for assessing the sensitivity of both primary and secondary analyses to missing at random and missing completely at random assumptions. First, for individuals that withdraw from the study or have missing visits, we will collect information on the reasons for those missed visits. That information, coupled with data collected from earlier visits will be used to develop comparisons of the two treatment arms using pattern mixture models. For the second approach, we will use multiple imputation based on a model conditional on baseline covariates, treatment group, and all previous measures. Separate imputation models will be used for the two groups.

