9.6 Data Analyses

Specific Aim 1: Determine whether a mind/body therapy (hypnotherapy) is as, or is more effective and durable, in treating urgency urinary incontinence (UUI) than a non-mind/body treatment (pharmacotherapy)

Statistical Analysis: Improvement between hypnotherapy and controls will be compared at baseline and followup at 2, 6, 12 months. Because of the possibility that a number of subjects may be cured (i.e. report "0" urgency incontinence episodes) at follow-up on voiding diary, we will use a zero inflated Poisson (ZIP) generalized linear mixed model for the analysis and compare groups' urgency incontinence episodes. The ZIP model analysis is proposed because the data are expected to be relatively low counts with the potential of a large numbers of zeroes, particularly at 2 and 6 months, in excess of those allowed by the Poisson. Simple conversion to percent change will not correct the discrete nature of the data ("cures" become 100 percent change rather than 0 UUI count at 2 months), and standard least squares methods will not be appropriate. If there is no inflation at 0, i.e. standard Poisson regression is appropriate, then the associated log-linear model yields percent change as a natural parameter (by exponentiating the group effect). If there is significant inflation at 0, the confidence interval for percent change in the mean will be constructed by combining the two portions of the model with standard error estimated by the delta method, and checked via bootstrap methods. We will be able to derive mean UUI episodes as well as mean % change in UUI episodes following ZIP model analyses. All other parameters, which are normally distributed or continuous variables, will be compared using a linear mixed model analysis. It is unlikely that there will baseline differences between groups, given that this is a randomized controlled trial. If baseline differences between groups are found (e.g. incontinence duration, coexisting illnesses, prior treatment), appropriate variables will be added to the analysis as covariates. We will include pre-treatment patient expectations and hypnotic susceptibility as covariates in the analysis and determine if they are independent predictors of treatment response. We will not exclude subjects based on hypnotic susceptibility to increase the generalizability of our findings. We anticipate subjects' pre-treatment expectations will be an independent predictor of improvement in urgency incontinence & guestionnaire scores (the previously determined sample size is adequately powered to find a relatively small partial R² of .05¹³ between expectations and outcomes). The primary outcome measure will be change in UUI episodes from baseline to follow-up with a between group comparison, and not "cure". However, the term "cure" may be used for secondary analyses. As such, our definition of "cure" will be: absence of UUI episodes recorded on voiding diaries at 2, 6 and 12 month follow-up. Primary analyses will be performed using intention to treat. A per protocol analysis will also be performed; those who did not comply with the study interventions, extensively used other concomitant treatments known to improve UUI (e.g. used other UUI medications, underwent sacral neuro-modulation), or missed multiple treatment sessions will be considered to have been off protocol subjects. Similar analyses will be performed comparing group differences in change in questionnaire scores while accounting for covariates such as pain/interstitial cystitis (based on VAS pain scale and IC questionnaire) or bowel abnormalities (based on the CRADI-8), medical history and demographic variables (based on the medical history and demographic sheets) on the outcomes.

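### The missing-data sensitivity analyses leave out the 6- and 12-month diaries of a woman who misses the primary 2-month diary but returns later

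*Combined protocol and SAP*

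**What the plan says.** The primary outcome in section 9.1 is "Between group differences in change in UUI episodes for Specific Aim 1 at 2 month follow-up based on 3 day voiding diaries". Women are seen at 2, 6 and 12 months, so the 2-month diary is the first after baseline. Section 6.2.5 keeps women in follow-up after they stop or do not comply with treatment: "All subjects will have follow-up assessments irrespective whether they discontinue study interventions or are non-compliant with interventions". Later diaries can therefore exist for a woman whose 2-month diary is missing.

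Section 9.3 (Missing Data) describes two kinds of loss. One is withdrawal or loss to follow-up, with nothing measured afterwards. The other is a missed visit, of which it says "The missing data from this second group will follow an intermittent pattern". It then names two sensitivity strategies:

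- Reasons for missed visits are collected. "That information, coupled with data collected from earlier visits will be used to develop comparisons of the two treatment arms using pattern mixture models".
- The second is "multiple imputation based on a model conditional on baseline covariates, treatment group, and all previous measures", with a separate imputation model for each arm.

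The primary analysis in section 9.3 treats missing observations as missing at random. Section 9.6 specifies a zero-inflated Poisson mixed model, in an analysis where the groups "will be compared at baseline and followup at 2, 6, 12 months". Section 6.2.4 and the schedule in section 6.1 show incontinence logs collected at the weekly treatment visits.

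**The concern.** Conditioning on earlier measures suits permanent withdrawal, because nothing comes later. It does not suit the intermittent pattern that the same section predicts. For a missing 2-month diary, the earlier measures are the baseline data and at most the weekly logs. The woman's own 6- and 12-month diaries are observed outcome data that bear on the missing value, and neither strategy names them.

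Two things are at stake. First, missing at random is easier to defend when all observed data are used. If missing the 2-month visit is related to how a woman is doing, and her later diaries show it, imputation that ignores them is biased where imputation that uses them is not. Second, if the section 9.6 mixed model is fitted jointly to all three visits, it uses the later diaries through its random effects. The check would then rest on less information than the analysis it tests. A difference between the two results could come from the missingness assumption or from the diaries left out, and a reader could not tell which.

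**Working it through.** **The plan's own figures.** Section 9.2 gives 52 analysable women per arm after 33% attrition: 152 × (1 − 0.33) / 2 = 50.9, which agrees within two women. No SD is stated, so it is back-solved from SD = (true difference + margin) / [(1.960 + 0.842) × √(2/n)], at one-sided alpha 0.025 and 80% power:

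- n = 52, difference 9, margin 5: 14 / (2.802 × 0.1961) = 25.5.
- n = 60, difference 8, margin 5: 13 / (2.802 × 0.1826) = 25.4.

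The two statements agree, and 25.4 points is used below.

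**Which data each strategy uses for a woman with no 2-month diary who returns later**

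| Data | Multiple imputation | Pattern mixture |
|---|---|---|
| Baseline | yes | yes |
| Weekly logs | if counted as previous measures | if counted as earlier visits |
| Reasons for missed visits | not named | yes |
| 6- and 12-month diaries | no | not named |

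**Illustration. All correlations and mechanisms are assumptions; the documents give none.** The 2-month outcome is correlated 0.3 with baseline, 0.7 with month 6 and 0.6 with month 12. Months 6 and 12 are correlated 0.7 with each other and 0.3 with baseline. Where a late weekly log is added, it is correlated 0.7 with month 2, 0.3 with baseline, 0.6 with month 6 and 0.5 with month 12.

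The share of variance in the missing value that is explained is R² = c′S⁻¹c, where c holds the correlations of the predictors with month 2 and S their correlations with each other:

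- Baseline alone: 0.3² = 0.09.
- Baseline and later diaries: 0.52.
- Baseline and late log: 0.50.
- Baseline, late log and later diaries: 0.62.

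With weaker later correlations (0.5 and 0.4), baseline and later diaries explain about 0.3. In the case most favourable to the plan (all correlations 0.76, the diary intra-class correlation quoted in section 9.1), R² still rises from 0.58 to 0.69 without any log.

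The bias was simulated with 400,000 normally distributed records in one arm. The 2-month diary was removed in 5-15% of them by a logistic model (log-odds 0.7-1.0 per SD), and the gap was filled by regression on each set of predictors. Shift in that arm's mean, in points:

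| Predictors | Gap depends on later response | Gap depends on unseen 2-month value |
|---|---|---|
| Baseline | 0.5-2.1 | 0.8-3.1 |
| Baseline + late log | 0.2-1.0 | 0.4-1.8 |
| Baseline + 6 and 12 months | about 0 | 0.4-1.7 |
| All of these | about 0 | 0.3-1.3 |

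**The case against.** The strongest reply is that the weekly logs already do much of the work. The last log falls within weeks of the 2-month diary, while the 6-month diary is months away, and the phrase used in section 9.3 can reasonably cover the logs. With one late log at correlation 0.7, the log and the later diaries do about equally well when the gap depends on the unseen value. This stands: figures from baseline alone are a worst case. But a woman who misses the 2-month visit may also lack late logs, and adding the later diaries still removes the remaining 0.2-1.0 points in the later-response case and raises R² from 0.50 to 0.62.

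It is also fair that the fall to about 0 is built in, because missingness was made to depend on the diaries that are then added. The 5-15% gap rate has no source either: section 9.3 aims for under 10% missing data overall, and attributes intermittent gaps to events such as illness or family emergencies.

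Three stronger readings are tempting, and the documents do not support them:

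- *The primary result discards the later diaries.* The wording concerns only the sensitivity analyses. The primary analysis is a mixed model under missing at random.
- *Both checks impute from earlier visits alone.* Only the second strategy imputes. The first is a pattern-mixture comparison that also uses the reasons for missed visits.
- *A shift of up to 2 points uses up much of the 5-point margin.* The shift is in one arm, while the margin applies to a difference. Equal shifts cancel, and the documents do not establish that the arms would differ in this respect.

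**Conclusion.** The point stands as a minor one. Section 9.3 predicts intermittent gaps and then states a rule that leaves out later diaries, and no other section adds them. Replacing a stated rule with a better one is more than a request for detail.

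Its reach is limited to the two sensitivity analyses, and within them to women who miss a visit and return; how many is not stated. That the check uses less information than the primary analysis depends on a joint fit to 2, 6 and 12 months. This is the natural reading of section 9.6, but it is not stated outright.

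The size is illustrative: a one-arm shift of about 0.5-2.1 points from baseline alone, or 0.2-1.0 with a late log, falling to about 0 when the gap depends on later response and only partly reduced when it depends on the unseen value. These figures rest on the back-solved SD, the assumed correlations and gap rates, and normal rather than zero-heavy count data. A material effect on the non-inferiority conclusion has not been shown.

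**What to change.** Replace the multiple-imputation sentence in section 9.3 with wording such as:

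> UUI episodes at 2, 6 and 12 months will be imputed jointly and separately by arm, with a model suited to counts with many zeros. Each missing visit will be conditional on baseline covariates, the weekly incontinence logs and all other observed visits, earlier and later.

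Use the same information for intermittent gaps in the pattern-mixture analysis. It would also help to say in section 9.6 whether the mixed model is fitted jointly to the three visits.

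The cost is small: no new data, no change in sample size, and the by-arm imputation stays. The imputation model becomes somewhat larger for about 76 women per arm (152 / 2), and fitting it to zero-heavy counts needs care. Later diaries may also reflect treatment changes after month 2, such as stopped medication, off-protocol therapy or the optional extra hypnotherapy session. That can weaken their link to the 2-month value and should be acknowledged when the result is reported.

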9.4 Interim Analyses and Stopping Rules

Stopping Rules

This is a low risk study as both interventions are low risk; pharmacotherapy is a standard, accepted treatment of UUI and hypnotherapy is considered a low risk intervention as hypnosis can only occur in subjects who allow themselves to be hypnotized (i.e. the hypnotic state cannot be forced upon individual). Nonetheless, in the unlikely event that the following situations occur, the study will be stopped prior to completion if: (1) any of the interventions are associated with SAEs attributable to the interventions that call into question the safety of the interventions (likelihood is extremely low) (2) difficulty in study recruitment or retention will significantly impact the ability to evaluate the study endpoints (likelihood is extremely low) (3) any new information becomes available during the trial that necessitates stopping the trial (likelihood is extraordinarily low).

In the unlikely event that >33% of study subjects report that they experience serious emotional upset from study participation the study will be suspended and a review will occur. Serious emotional upset includes inability to work or events that would necessitate evaluation by a physician or care provider. It is unlikely that this will occur as we have had 0/17 subjects in our pilot study evaluating hypnotherapy treatments in OAB subjects report physical or emotional upset from study participation. However, it is highly unlikely that hypnotherapy could potentially unmask or de-repress significant emotional upset (e.g. hysteria, uncontrollable anger or hostility) in subjects. The potential for this occurring will be minimized by excluding subjects with a history of schizophrenia or untreated bipolar disorder and by having the hypnotherapist guide the sessions and terminate sessions if subjects are beginning to show signs of undue duress during hypnotherapy. A report of a subject experiencing serious emotional upset from study participation will result in a meeting of the PIs and review of the issues surrounding its occurrence. The PIs and Study coordinator will generate a report, assess whether it was

preventable, and develop an action plan to prevent recurrence including potential protocol revision and this report will be given the DSMB. The likelihood of this occurring is very small. Sporadic occurrence of emotional upset is always possible in any setting, and if an individual treated with hypnotherapy notes this occurrence which she attributes to hypnotherapy, the intervention will be terminated. However, we believe that if a third of subjects complain of this issue, the study should be halted until the circumstances surrounding its occurrence are investigated. Other hypnotherapy studies have not reported this occurring; however, we believe that it is prudent to consider this as a possibility and to prepare for it as a possibility, although highly unlikely. The study would also be stopped if there were statistically significant differences in SAEs (as defined in section 7.3) definitely attributable to the interventions (hypnotherapy or pharmacotherapy). The medications in the pharmacotherapy arm, considered standard of care treatments, have undergone rigorous FDA approval, and it would be highly unlikely that these events would occur.

9.5 Outcomes

Outcomes documentation will not be reviewed and adjudicated by a committee. Outcomes will be analyzed by the Investigators and Study Statistician, [name], after the study is completed and the blind is broken using standard SAS® software on the Redcap® database maintained in a fashion consistent with UNM HRPO policy.

9.51 Primary Outcome

Specific Aim 1: Determine whether a mind/body therapy (hypnotherapy) is as, or is more effective and durable, in treating urgency urinary incontinence (UUI) than a non-mind/body treatment (pharmacotherapy)

The primary outcome for the analysis of Objective 1 will be change in UUI episodes based on 3 day voiding diaries for the hypnotherapy group compared to the pharmacotherapy group at 2 month follow-up (See flow Diagrams Section 5. "Study Interventions")

Specific Aim 2: Determine whether hypnotherapy treatment of UUI (urgency urinary incontinence) is associated with greater modification of brain activation and connectivity on functional MRI than that which occurs following pharmacotherapy.

Hypothesis 2.2. Among patients with urgency incontinence, hypnotherapy will decrease hyper-activation of the limbic cortex in response to bladder distension and/or modulate functional connectivity within the limbic system. Moreover, normalization of hyper-activation and connectivity will be greater in hypnotherapy compared to pharmacotherapy

The primary outcome is to evaluate whether UUI subjects treated with hypnotherapy have decreased hyperactivation of the limbic cortex (ACC and insula) in response to bladder distention and/or modulation in functional connectivity within the limbic cortex in response to bladder distension compared to subjects treated with pharmacotherapy. This will be obtained after the subjects finish their 8 weeks of either pharmacotherapy or hypnotherapy (Visit 12; see flow Diagrams Section 5. "Study Interventions')

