Primary outcome measures for Objective 2.2 will be pharmacotherapy treated subject versus hypnotherapy treated subject change in task related activation of the insula and anterior cingulate cortex and change in resting functional connectivity between these groups. The test-retest reliability of fMRI results have been evaluated in multiple settings including within multicenter research consortiums.⁸² Assessment of the reliability of brain activation within regions of interest has shown intra-class correlation coefficients frequently greater than 0.8.³⁰ Test-retest reliability has also been shown to be preserved over a one year time span.³

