Statistical Analysis 2.2 Pre- and Post-Treatment measurements in patients with UUI: Prior functional MRI analysis during the hypnotic state has shown complete suppression of anterior cingulate cortex activation in response to pain.⁵⁵ However, the magnitude of suppression of anterior cingulate cortex or insula signal outside the hypnotic state has not been studied. Current study size will be able to detect differences between pre and post treatment signal within a treatment group with an effect size of approximately 0.5 and a power of 0.8. Minimal effect size would be approximately equivalent to a 60% decrease in the excess (above normative control) anterior cingulate cortex and insula signal. We predict a main effect of time, suggesting that both treatments are effective in reducing activity within the anterior cingulate cortex and insula. However, we also predict a significant Group x Time interaction, indicating that that change in activity will be greater for the hypnotherapy relative to the pharmacotherapy group. Minimum detectable effect size for the Group X Time interaction is 0.7 with power of 0.8 and alpha of 0.05. Similar to brain activation, no prior data is available in the literature regarding the expected change in waking state connectivity following hypnotherapy. Current study size will be able to detect within-group differences between pre and post treatment signal with a minimal effect size of approximately 0.5 and a power

of 0.8, much lower than the observed effect size of >3 in our pilot study. The minimum effect size would be reached with a 15% decrement in anterior cingulate cortex to insula connectivity. As for evoked activity we predict both a main effect of time, and predict a significant Group x Time interaction, indicating that change in functional connectivity will be greater for the hypnotherapy relative to the pharmacotherapy group. Minimum detectable effect size for the Group X Time interaction is 0.7 with power of 0.8 and alpha of 0.05. This minimum effect size will be reached when between group differences in anterior cingulate cortex to insula connectivity are \geq 30%.

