Statistical Analysis of 2.1 Normative controls vs. urgency incontinence subjects: Regions of interest containing the insula and anterior cingulate cortex will be analyzed in keeping with our a priori hypothesis using two way ANCOVA with group as the between subject's factor and age as a covariate. Pre-treatment β weights for both bladder filling and urgency regressor effect on anterior cingulate cortex and insula signal among normative subjects will be compared to the effect on signal in urgency incontinence subjects. The planned study size allows detection of differences between groups with an effect size >0.8 with power of 0.8, smaller than the observed effect size in our pilot study.⁴³ The effect size observed in our pilot study (Cohen's d ranged from 0.8 to 1.5) suggests that the study will be adequately powered (greater than 0.8) to reject the null hypothesis at an alpha=0.05. In addition to analysis of prior regions of interest, group wise whole brain contrast will also be performed using an identical statistical model. False positives will be corrected at a significance threshold corresponding to p <.005 applied in combination with a minimum cluster size threshold of 32 native voxels (p < 0.05), parameters derived from 10,000 Monte Carlo simulations.⁸⁰ Analysis of between group differences in functional connectivity will be performed in a similar fashion to that used to analyze brain activation evoked by bladder filling and emptying. The large observed effect size in our preliminary data (>3) suggests that the sample size used for proposed analysis of evoked potentials will be more than adequate.

Although the principal purpose of this analysis is to further explore the pathophysiologic underpinnings of UUI within the brain, we will also explore the use of evoked potentials and functional connectivity as a biomarker for UUI. Towards that end we will construct receiver operator curves (ROCs) based on fMRI output from controls and patients with UUI.

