Statistical Analysis 2.2 Pre- and Post-Treatment measurements in patients with UUI: Efficacy of hypnotherapy and pharmacotherapy on anterior cingulate cortex and right insula activation will be compared using a 2x2 (Group x Time) mixed model ANCOVA to correct for potential differences in group characteristics (e.g. age). Analysis of treatment effect will be focused on the anterior cingulate cortex and insula based on preliminary data that suggests the effect size for change in activation will be highest in these regions. Prior functional MRI analysis during the hypnotic state has shown complete suppression of anterior cingulate cortex activation in response to pain.⁵⁵ However, the magnitude of suppression of anterior cingulate cortex or insula signal outside the hypnotic state has not been studied. Current study size will be able to detect differences between pre and post treatment signal within a treatment group with an effect size of approximately 0.5 and a power of 0.8. Minimal effect size would be approximately equivalent to a 60% decrease in the excess (above normative control) anterior cingulate cortex and insula signal. We predict a main effect of time, suggesting that both treatments are effective in reducing activity within the anterior cingulate cortex and insula. However, we also predict a significant Group x Time interaction, indicating that that change in activity will be greater for the hypnotherapy relative to the pharmacotherapy group. Minimum detectable effect size for the Group X Time interaction is 0.7 with power of 0.8 and alpha of 0.05. Simple effects tests will also be conducted to ensure that randomization to treatment arm was successful (i.e. no differences in baseline activity across the two groups).

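### The Aim 2 fMRI primary outcome is defined inconsistently and has no success or multiplicity rule, so its false-positive rate is not determined

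*Combined protocol and SAP*

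**What the plan says.** The between-treatment fMRI comparison is a primary objective (section 1.1.2) and a primary outcome (sections 3, 9.1 and 9.51). Its content differs by place:

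- **Sections 3 and 9.1, outcome lists:** "Between group differences in change in activation of limbic cortex and brain connectivity following treatment for Specific Aim 2". The link is *and*; no region, side or type of connectivity is named.
- **Section 9.1, Objective 2.2:** "change in task related activation of the insula and anterior cingulate cortex and change in resting functional connectivity between these groups". The link is again *and*; connectivity is measured at rest.
- **Section 9.51, Hypothesis 2.2:** the between-group sentence says that "normalization of hyper-activation and connectivity will be greater in hypnotherapy compared to pharmacotherapy", also with *and*.
- **Section 9.51, the outcome itself:** lower activation of the ACC and insula "and/or modulation in functional connectivity within the limbic cortex in response to bladder distension". The link becomes *and/or*, and connectivity is tied to bladder filling.
- **Section 9.6, Statistical Analysis 2.2:** "anterior cingulate cortex and right insula activation will be compared using a 2x2 (Group x Time) mixed model ANCOVA". The insula is now the right one; the next sentence drops the side again.

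On error rates, section 9.6 states for activation: "Minimum detectable effect size for the Group X Time interaction is 0.7 with power of 0.8 and alpha of 0.05". The connectivity interaction receives the same full level in section 9.2: "power of 0.8 and alpha of 0.05. This minimum effect size will be reached when between group differences in anterior cingulate cortex". No order, split or adjustment is given for the 2.2 comparison. The only correction for multiple testing is the voxel and cluster threshold for the whole-brain contrast, written under Hypothesis 2.1.

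On regressors, the Task A model in section 5.1 has one for urge and one for filling and emptying. Analysis 2.1 in section 9.6 uses effects "for both bladder filling and urgency regressor effect on anterior cingulate cortex and insula signal". Analysis 2.2 does not say which regressor it tests.

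**The concern.** A primary outcome needs one definition and one rule for success. Here the components, the way they combine, the side of the insula, the task behind connectivity and the regressor are all open. If one significant component is enough and each is tested at 0.05, the error rate for the whole outcome exceeds 5%.

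Section 9.5 places the outcome analysis after the blind is broken, and nothing in the text binds the analyst to one version before then. At stake is the claim that hypnotherapy changes brain function more than medication does. Section 9.6 intends to draw a mechanistic conclusion from that claim, attributing the brain changes to mind-body therapy.

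**Working it through.** **1. The plan's own figure.** Inputs: up to 60 analysable UUI datasets (Précis), about half per treatment (section 3), so 30 per arm; alpha 0.05, power 0.80, detectable effect 0.7 (section 9.6). I assume a two-sided test and an effect standardised on the change score; the plan states neither.

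- Detectable effect = (1.960 + 0.842) × √(2/30) = 0.723 by the normal approximation, or 0.736 by the t distribution. Both round to 0.7.
- Power at exactly 0.7 = Φ(0.7 × √(30/2) − 1.960) = Φ(0.751) = 0.774, or 0.760 by the t distribution.

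The stated 0.7 therefore agrees, after rounding, with a single test at the full two-sided 0.05. It leaves no room for sharing alpha.

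**2. Number of tests.** The plan gives no count. The readings are:

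- two: activation, connectivity;
- three: ACC, insula, connectivity;
- five: 2 regions × 2 regressors + connectivity. This carries the two regressors over from analysis 2.1.

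**3. Chance of at least one false positive if any component suffices.** For k independent tests this is 1 − 0.95^k. Correlated cases come from simulating equicorrelated normal statistics (1,000,000 draws); the correlations are assumptions.

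| Tests | Independent | r = 0.5 | r = 0.7 |
|---|---|---|---|
| 2 | 9.75% | 9.0% | 8.3% |
| 3 | 14.3% | 12.5% | 10.9% |
| 5 | 22.6% | 18.3% | 14.9% |

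**4. Only results favouring hypnotherapy count.** Each test then has 0.025 in that direction, so the rate is 1 − 0.975^k when independent: 4.9%, 7.3% and 11.9% for 2, 3 and 5 tests. At r = 0.7 it is 4.2%, 5.4% and 7.5%. The nominal level is now 2.5%, so the relative inflation is much the same.

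**5. All components required.** With no true effects, independent tests give 0.05² = 0.25% for two and 0.05³ = 0.0125% for three. At r = 0.7 the simulation gives 1.7% and 0.9%. There is no inflation. Power falls: if each test has 0.80 and they are independent, joint power is 0.80² = 0.64 for two and 0.80³ = 0.51 for three.

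**The case against.** The best defence is that the *and/or* belongs to one sentence. Both outcome lists, Objective 2.2 and the between-group sentence of Hypothesis 2.2 all use *and*. Even the section 9.51 sentence joins the two regions with *and*, so treating either region alone as success is a further inference. If every component is required, step 5 applies. This stands as a limit on the size of the problem. It does not supply a rule, because the *and* passages mostly list outcomes and none states what counts as success.

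A reader might infer that the false-positive rate simply is 11–23%. The documents do not support that. They fix neither the number of tests nor their correlation. The upper end needs two regressors, which are specified only for the comparison with controls. The 0.05 appears only in power statements; it is the natural reading, but not a stated rule.

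Some of the differences in definition are also milder than they look. The right insula is named once. The connectivity text in sections 9.2 and 9.6 points to a single pair, ACC to insula. Section 5.1 combines the resting Task B data with Task A results for connectivity, so rest versus distension is not a clean contradiction. These points still need one consistent wording.

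Finally, sections 9.2 and 9.6 describe the principal purpose of analysis 2.2 as exploring mechanism. That lowers the stakes, but the primary label and the separate power statements remain.

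**Conclusion.** The point holds as a gap in specification with a conditional effect on error. The Aim 2 primary outcome is defined in conflicting ways and has no success or multiplicity rule.

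If any component counts at two-sided 0.05, the chance of at least one false positive is about 8–10% for two tests and 11–14% for three, at correlations from 0.7 to 0. It is 15–23% only if both Task A regressors are tested as well. The one-directional and all-required readings lower this as shown above.

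A reader might also infer that the analysts will choose a version after seeing the results. The documents show only that the text leaves that choice open; fMRI interpretation is planned blind to allocation. Aim 2 is labelled primary but is described as mainly mechanistic, and none of this touches the Aim 1 non-inferiority conclusion. The text should be corrected, but the gap does not undermine the trial.

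**What to change.** Before the blind is broken:

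- Make sections 9.1, 9.51 and 9.6 (and the list in section 3) name the same region and side, the same Task A regressor, and one connectivity measure with its task.
- Replace *and/or* with a fixed order for the Group x Time effects. Each is tested at 0.05 only if the one before it succeeded.
- State whether the tests are two-sided, and label all other regions, regressors and connectivity measures exploratory.

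This changes wording only. The first test keeps its full power. The price is that a failed first test blocks formal claims on later ones.

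Holm across the named set is an alternative with a real cost. At 30 per arm and an effect of 0.7, power at the first step falls from about 76% to about 60% with three tests (0.05/3 = 0.0167) and 52% with five (0.05/5 = 0.01). Restoring 80% at those levels would need about 43 and 48 per arm, against the 30 planned for analysis. Section 11.2 says enrolment is complete, so a larger sample is not a practical remedy. The fixed order is the better choice here.
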